## **Fear Extinction Retention Experiment**

The fear extinction retention experiment will occur on three separate days prior to treatment. Participants will undergo conditioning procedures on Day 1, extinction learning on Day 2, and extinction recall and fear renewal on Day 3. Day 1 and Day 3 sessions will take place no more than seven days apart. DCS or placebo will be administered immediately prior to the Day 2 procedures to examine whether DCS enhances extinction recall and reduces fear renewal on Day 3.

Experiment procedures are based on a previously validated fear conditioning and extinction paradigm. During each portion of the experiment, recording electrodes will be attached to the palm of the participant's left hand to measure skin conductance response (SCR), and stimulating electrodes will be connected to two fingers of the participant's right hand to deliver an electric shock. SCR will be measured through a 9-mm (sensor diameter) Sensor Medics Ag/AgCl electrodes. For each trial, participants will view a computer monitor with an image of one of two different rooms containing an unlit lamp for 6 seconds. The lamp will then be "switched on" to one of two colors for 12 seconds, which will serve as the conditioned stimulus (CS). One of the two colors will be paired with an electric shock (the unconditioned stimulus, or US), while the other color will not. The shock will have been previously selected by the participant to be "highly annoying but not painful" and delivered for 500 millisecond through electrodes attached to the second and third finger of the right hand. The inter-trial interval will last an average of 15 seconds. The stimulating electrodes will remain attached to the fingertips throughout the experiment, but the US will be administered only during the Conditioning session on Day 1.

On Day 1, the to-be CS+ and the to-be CS- (four trials of each) will be presented within each room in a counterbalanced manner without presentation of the US (Habituation phase). The Conditioning phase will follow with five CS+ trials that will be immediately followed by the US (100% reinforcement), and five CS- trials (i.e., not followed by shock). All conditioning trials will use the same context (one of the two rooms). On Day 2 (Extinction phase), five CS+ trials and five CS- trials will be presented within the extinction context (the room not used during conditioning) with no US presentation. Day 3 consists of the Extinction Recall phase and the Renewal phase. Extinction Recall is identical to the Extinction phase on day 2, while Renewal is identical to the Conditioning phase except without presentation of the US.

For each trial, SCR will be calculated by taking the difference between the highest skin conductance level (SCL) during each 12-second CS+/CS- presentation and the mean SCL during the 2 seconds immediately preceding that trial. The SCR for the CS- will be subtracted from the SCR for the CS+ to create a differential SCR. Performance during Extinction Training and Recall will be assessed by comparing SCR during CS+ trials on Day 2 and 3 with the maximum SCR during the Conditioning phase. Our main outcome of interest will be Extinction Retention, for which we will calculate an extinction retention index based on the ratio of the mean SCR during the first two trials of the Extinction Recall phase to the largest SCR during the Day 1 Conditioning phase. This ratio will be multiplied by 100 to

yield a percentage of the maximum conditioned response, and this value will be subtracted from 100% to yield the extinction retention index.

### Therapy Procedures

Consistent with prior clinical trials, we will use a 5-session group CBT protocol emphasizing repeated exposure practice. Each group will consist of 4–6 patients and 2 therapists, who will be PhDs or advanced, trained doctoral students supervised by the PIs. In the first session (60 minutes), patients will be introduced to the cognitive-behavioral model of SAD and provided a rationale for treatment with exposure therapy. Sessions 2–5 (90 minutes each) will consist of increasingly difficult public speaking exposure tasks in which each participant in the group will give an impromptu speech on a topic chosen by the therapist in front of the other group members, confederates and a video camera. Video recordings of each exposure will then be reviewed, and participants will compare pre-exposure predictions about their behavior and appearance during the speech task with their actual performance. Participants will be encouraged to apply home-practice strategies.

### Pill Administration

Following prior research demonstrating DCS to augment exposure therapy, DCS will be administered in 50 mg doses. Administration of DCS at such a dose has been shown to have a benign side effect profile, and increasing the dose to as high as 500 mg has not shown additive effect in enhancing exposure-based treatment. DCS and placebo capsules will be identical in appearance and administered by staff blind to study condition and not involved in the assessment or treatment of participants. Participants in the fear extinction retention experiment will take one study pill (i.e., 50 mg DCS or placebo) immediately before Day 2 of the experiment.

The pharmacist will fill three bottles (with one pill type in each) for each patient for each exposure session according to the schedule in Table 2. Patient, therapist, and staff will be blind to the drug condition (DCS vs. placebo) at pre-exposure; and therapists and patients will be blind to the drug condition at post-exposure. Regardless of study condition, research staff will administer a pill (Pill 1) to each participant one-hour before the exposure session and administer a second pill (Pill 2) immediately after the exposure session. In the tailored administration condition, the selection of Pill 2 will be guided by the end fear level. Specifically, DCS will be administered if the end fear is  $\leq 40$  (of 100) on the Subjective Units of Distress Scale (SUDS), whereas placebo will be selected if the end fear is  $> 40$ . A cutoff of 40 and below was selected based on results of our prior clinical trial, which demonstrated that when end SUDS ratings were below 47, DCS showed an advantage over placebo. Two prior studies using the same 5-session CBT protocol found that mean end SUDS ratings were 49.5 ( $SD = 19.2$ ) and 39.1 ( $SD = 17.7$ ). In the latter study, 85% of patients had at least one end SUDS rating of 40 or below, and 67.5% had at least 2 end SUDS ratings of 40 or below, demonstrating that there is sufficient variability in end fear ratings to justify the examination of tailored and non-tailored post-session DCS administration.

Pill administration schedule

Table 2

Condition	Pre-exposure (1 st Pill)	Post-exposure (2 nd Pill)	
		If SUDS $\leq 40$	If SUDS $> 40$
1. Pre-session DCS	DCS	PBO	PBO
2. Placebo	PBO	PBO	PBO
3. Non-tailored post-session DCS	PBO	DCS	DCS
4. Tailored administration	PBO	DCS	PBO

Note: The Table shows the pill administration schedule. All patients receive 2 pills, one before and one after the exposure session. Depending on experimental condition and SUDS at end of exposure, patients receive one of 4 pill combinations. SUDS: Subjective Units of Distress Scale (rated 1–100); PBO: placebo; DCS: D-cycloserine (50 mg).

## Outcome Measures

The administration of assessments is detailed in Table 3.

Schedule of Assessments

**Table 3**

Measures	Screening	Baseline	Each Session	Post-treatment	1 mo. Follow-up	3 mo. Follow-up
SCID or ADIS	X					
Medical Screening	X					
Primary Outcomes						
LSAS	X	X	X	X	X	X
SPD-SC Form	X	X	X	X	X	X
Fear Extinction Paradigm (optional)	X a					
Secondary Outcomes						
MADRS	X	X	X	X	X	X
Q-LES-Q		X		X	X	X
ASC		X	X	X	X	X
SAFE		X	X	X	X	X
SAQ		X		X	X	X
Exposure Success						
SUDS			X b			
Heart Rate			X b			
Salivary Cortisol and Alpha Amylase			X b			
Moderators and Predictors						
Demographics	X					
NEO-FFI		X				
PSQI		X				
CSD			X c			
Audio-recorded speech			X d			
CEQ			X e			
Adherence			X			

**Note:** ADIS = Anxiety Disorder Interview Schedule; SCID = Structured Clinical Interview for DSM Disorders; LSAS = Liebowitz Social Anxiety Scale; SPD-SC Form = Social Phobic Disorders Severity and Change Form; ASC = Appraisal of Social Concerns; SAFE = Subtle Avoidance Frequency Examination; SAQ = Social Anxiety Questionnaire for Adults; MADRS = Montgomery Asberg Depression

Rating Scale; Q-LES-Q = Quality of Life Enjoyment and Satisfaction Questionnaire; PSQI = Pittsburgh Sleep Quality Index; CSD = Consensus Sleep Diary. SUDS = Subjective Units of Distress Scale; NEO-FFI = NEO Five Factor Inventory of Personality; CEQ = Credibility and Expectancy Questionnaire.

aThe fear extinction experiment will be scheduled after participants are deemed eligible from the ADIS/SCID and medical examination.

bIndicators of exposure success are measured during sessions 2–5 only, and salivary cortisol and alpha amylase samples will be collected at sessions 2 and 5 only.

cSubjects will complete the CSD the night before and the night after each session.

dRecordings of speeches from session 2 only will be saved for further analysis.

eThe CEQ will be administered after the first session only.

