## **Screening and Randomization**

Individuals interested in the study will undergo a psychiatric evaluation to evaluate psychiatric inclusion and exclusion criteria. Participants will be medically cleared by a study physician.

Participants in the optional fear extinction retention experiment will be randomized to receive either DCS or placebo prior to fear extinction procedures. For the clinical trial portion of the study, participants will be randomized to one of four conditions: 1) tailored post-session DCS, 2) unselective pre-session DCS, 3) unselective post-session DCS, or 4) pill placebo. The conditions of the fear extinction experiment will be equally distributed across the four clinical trial conditions such that participants will be equally likely to receive any combination of fear extinction condition and trial condition. Randomization will occur by site using variable-sized permuted block randomization (block sizes varying from 4 to 12). Randomization tables will be created before the first subject is run and sent to the study pharmacist to make the appropriate medication kits. The statistician will check the balance of randomization to control for any unbalanced factors.

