### **Outcome Analysis**

In order to evaluate whether tailored DCS administration produces superior outcomes to pre-session DCS, post-session DCS, and placebo, we will examine if the dummy variable contrasting tailored DCS to the relevant comparison condition is a significant predictor of the intercept. We will alternately "center" the "assessment week" variable at either posttreatment, 1-mo FU, or 3-mo FU to test for significant differences between conditions at each of these time points.

We will also examine a number of possible moderators of the potential superiority of tailored DCS over the comparison conditions (and, secondarily, of the superiority of pre-and post-DCS administration over PBO). We will use the Fournier approach to identify important moderators. This approach uses an algorithmic method to select significant predictors and moderators within each group of potential moderators (e.g., demographics, clinical and personality characteristics). These selected moderators are then combined in a final analysis, which identifies moderators that are significant over and above the other potential moderators. This approach strikes a balance between testing each moderator separately (which substantially increases Type I error due to the multiple tests) and testing all moderators simultaneously (which may substantially increase the likelihood of Type II error).

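### Three measures taken after trial drug may have been given are listed as moderators or predictors, and no rule keeps them out of the moderator search

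*Combined protocol and SAP*

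**What the plan says.** Table 3 of the combined protocol and SAP groups several rows under "Moderators and Predictors". Demographics, NEO-FFI and PSQI are collected at screening or baseline. The other rows fall in the each-session column, with this timing:

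- **Sleep diary (CSD):** "Subjects will complete the CSD the night before and the night after each session".
- **Speech:** "Recordings of speeches from session 2 only will be saved for further analysis".
- **CEQ:** "The CEQ will be administered after the first session only".
- **Adherence:** marked for each session, with no definition.

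Under Therapy Procedures, session 1 is introductory and sessions 2–5 "will consist of increasingly difficult public speaking exposure tasks". Under Pill Administration, "research staff will administer a pill (Pill 1) to each participant one-hour before the exposure session", and Pill 2 follows straight after the session. Table 2 makes Pill 1 DCS in the pre-session arm and placebo in the other three arms.

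The Outcome Analysis section states: "We will also examine a number of possible moderators of the potential superiority of tailored DCS over the comparison conditions". Its Fournier procedure screens each group of candidates for significant predictors and moderators, then combines those selected in a final analysis. The examples it gives are of the baseline type. It sets no cut-off for when a candidate must be measured, and it does not say which Table 3 rows are predictors only.

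**The concern.** A moderator analysis asks whether the effect of treatment differs by a characteristic that treatment has not altered. From session 2 onward, adherence and sleep are recorded after trial drug may have been given, and so is the session-2 speech in one arm. If the drug or early response changes such a variable, an arm-by-variable interaction can no longer be read as moderation. The variable also distorts the arm contrast if it enters only as a predictor, because arms are then compared at equal values of something treatment has moved.

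At stake is what the moderator analysis can be used for. A variable known only after dosing cannot guide who should receive DCS at the outset, and an artefact in this model could be carried into a later study as a selection rule.

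**Working it through.** **Timing against drug**

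| Measure | Relation to exposure-session drug |
|---|---|
| CEQ, after session 1 | Before any exposure-session pill |
| Diary up to the night before session 2 | Before any exposure-session pill |
| Diary from the night after session 2 | After DCS in the pre-session and untailored post-session arms; in the tailored arm, after DCS only if end fear was 40 or below |
| Session-2 speech | After DCS in the pre-session arm; after placebo in the other three |
| Adherence from session 2 | During treatment in all arms; content undefined |

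The diary has a problem specific to this design. In the tailored arm DCS follows only low-fear sessions, while in the untailored post-session arm it follows every session. If DCS affects sleep, the link between sleep and exposure success can differ between these arms with no true moderation.

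**The plan's own figures.** The Power analysis section assumes five moderators and three contrasts: 5 × 3 = 15 interactions, as stated. Its detectable effect of d = .466 depends on variance components that the document does not give, so it can be neither reproduced nor called wrong. The point does not depend on it.

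**Inputs for the check.** "participants will be randomized to one of four conditions", so 156/4 = 39 per arm if equal. The model is a two-arm linear regression of outcome on arm, measure (centred) and their product, with no true moderation. Outcome and measure share a latent prognosis. All strengths are assumptions.

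**Bias in the arm contrast.** Let β be the within-arm slope of outcome on measure (SD units) and δ the drug's shift in the measure. The adjusted contrast is then the true contrast minus β × δ.

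- β = −0.3, δ = 0.5: bias = 0.3 × 0.5 = +0.15. A true effect of −0.30 is estimated as −0.15.
- Same β, δ = −0.5: bias = −0.15. The effect is estimated as −0.45.
- β = 0.5, δ = 0.3, 0.5, 0.8: bias = −0.15, −0.25, −0.40. Simulation gave −0.152, −0.249, −0.398.

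For scale, the plan equates d = .296 with 6.59 LSAS points, an implied SD of 6.59/0.296 = 22.3. If that SD applies, 0.15 SD is 0.15 × 22.3 = 3.3 points.

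**False interactions.** The slope in each arm is cov(outcome, measure)/var(measure). In the main setting both latent loadings are 0.7071, so the comparator slope is 0.7071 × 0.7071 = 0.50. Rates are from 8,000 runs at a nominal 5% (alpha is an assumption).

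| What treatment does to the measure | Slope in treated arm | Rejection rate |
|---|---|---|
| Nothing | 0.50 | 5.1% |
| Shifts the mean by 0.3, 0.5, 0.8 SD | 0.50 | 5.1%, 4.9%, 5.2% |
| Halves the link to prognosis | 0.25 | 20.8% |
| Removes the link | 0 | 62.5% |
| Noise SD × 1.5 | 0.5/(0.5 + 0.5 × 2.25) = 0.31 | 18.1% |
| Noise SD × 2 | 0.5/(0.5 + 0.5 × 4) = 0.20 | 38.0% |
| Raises it by 1.0 SD against a cap 0.5 SD above the comparator mean | simulated interaction +0.33 | 10.6% |

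With weaker assumed links the rate was 9.8% when the link was halved, and 12.8% in another setting where adherence tracked prognosis more strongly in one arm. With fear-dependent dosing as the only mechanism, the rate was about 5–10%, mostly near nominal, and contrast bias reached 0.19 SD.

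**The case against.** The strongest reply is that the plan never says these variables will be used as moderators. The heading is joint, the Fournier paragraph does not cite Table 3, its examples are baseline characteristics, and the speech footnote only says that recordings are kept for later use. That stands as far as it goes: a reader might infer that the plan commits to testing adherence, sleep and speech as moderators, and the text does not show that. But Table 3 is the only place that assigns variables to this role, the algorithm is the only analysis described for it, and it screens for both functions. Reading the rows as predictors only does not help, because a drug-affected predictor still biases the arm contrast.

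Four further limits stand:

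- **A drug effect on the measure is not enough for a false interaction.** A mean shift alone left the rate at 4.9–5.2%. The documents give no evidence that spread, link or ceiling would change, so the higher rates show what is possible and are not forecasts.
- **The direction of bias is unknown.** It would be wrong to say that adjustment removes part of the drug effect, since the opposite shift exaggerates it.
- **The speech is a narrower problem.** Tailored v untailored post-session and tailored v placebo are free of it. It touches tailored v pre-session and the secondary comparison of pre-session DCS with placebo.
- **Adherence is undefined, and staff give the pills.** That the drug changes adherence is an assumption.

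**Conclusion.** The concern holds in limited form. Followed as written, the plan allows drug-affected variables into the final moderator model and has no rule to stop it. The more robust harm is a biased arm contrast in that model: about 0.15 SD for a 0.5 SD drug shift when the outcome slope is 0.3, and 0.25 SD when the slope is 0.5, in either direction. Inflated interaction tests, about 10–20% or more against 5%, need the additional conditions above.

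These figures rest on assumed effect sizes and a two-arm, single-time-point regression. The planned multilevel model and the algorithm's selection step were not simulated. The document does not give the exact time of randomisation, so the argument rests on when drug is given.

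A reader might infer that the test of tailored DCS is compromised. It is not. That test compares randomised arms through three dummy variables in a separate growth model, without these measures. The moderator analysis is secondary, which makes this a change worth making and not a threat to the main result.

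**What to change.** Add one sentence to Outcome Analysis limiting the Fournier candidate set to variables measured before the first exposure-session pill (session 2): demographics, baseline clinical severity, NEO-FFI, PSQI, the CEQ after session 1, and sleep-diary entries up to the night before session 2. State that the Day 2 pill of the optional fear extinction experiment, planned for 96 participants, does not count for this cut-off. Otherwise the rule would exclude the CEQ and the whole diary for them. That pill is itself randomised, and Screening and Randomization spreads its two conditions equally over the four arms.

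In Table 3, move adherence, later diary entries and the session-2 speech to a separate heading for process measures. Analyse them descriptively or as mediators with the assumptions stated, keep them out of the moderator algorithm, and define adherence.

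The cost is one table heading and a short addition to the text, with no new data. The downside is that a few variables, including sleep after exposure sessions, leave the moderator search and can be studied only as exploratory process measures. The speech is also lost as a candidate for contrasts among the three arms where it precedes trial DCS; one rule for all contrasts is simpler and worth that loss.

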## Data Analysis

We will assess the equivalence of the treatment groups on key baseline variables and any variables that differ among groups will be used as covariates in the final analyses. We will examine missing data patterns, dropout rates, and distributional properties of measures and use transformations to improve distributions if necessary. We will use pattern mixture modeling to assess the effect of missing data. We will rerun our analyses coding for various missing data patterns (no missing data, sporadic

missing, dropouts, etc.) to determine 1) if missingness impacts our findings and 2) how the differences between treatment conditions depends on the missing data pattern.

We will use multilevel modeling (MLM) to evaluate the effect of condition on our continuous outcome measures (LSAS, SPD-SC severity, MADRS, QLES-Q) and generalized linear mixed modeling (GLMM, which is MLM with a logistic linking function) to examine DCS's effect on the dichotomous outcomes ("response" and "remission," explained below). MLM is the recommended method for analyzing longitudinal psychiatric data, easily accommodates missing data, and allows inclusion of all subjects in the analysis even if they drop out. In our MLM analyses, the repeated assessments over time will be nested within individuals, which will be nested within treatment cohort, thereby appropriately accounting for correlated scores within cohorts. We will use a piecewise growth curve model, separately modeling change over time during treatment and follow-up. We will test for quadratic trends and include them if significant. Other non-linear models (e.g., exponential models) will be also be tested, and the model that best fits the data (based on AIC and BIC) will be used. Our "time" variable in these models will be coded as "assessment week" and will reflect the number of weeks since baseline. Using this model, we can test differences between tailored DCS administration and the 3 comparison groups (pre-session DCS, post-session DCS, and placebo) by including 3 dummy coded variables as predictors of the growth curve parameters. Each dummy variable will contrast tailored DCS to each of the other 3 conditions.

### **Definition of Treatment Response and Remission**

Treatment "response" is based on the SPD-SC and is defined by an overall change score of 2 (much improved) or 1 (very much improved) as compared to the pre-treatment assessment. "Remission" is defined as an SPD-SC of 2 or 1 and an LSAS total score of < 30. This LSAS cutoff score is supported by a study of 364 patients that used receiver-operating characteristics in diagnosing SAD, and has generally been adopted as the boundary between remitted and symptomatic patients. It should be noted that the goal of this study is to determine effect size estimates for these gold-standard response and remission outcomes. Detecting differences on these dichotomous outcomes would require a very large sample size, and thus these estimates will be used to evaluate whether a larger- scale trial is warranted.

